10.6.2 Causal Relationship of Adverse Events to Investigational Medicinal Products

Medical judgment should be used to determine the cause of the AE considering all relevant factors such as, but not limited to, the underlying study indication, coexisting disease,

concomitant medication, relevant history, pattern of the AE, temporal relationship to the study medication, dechallenge or rechallenge.

Not Related

- An AE that is clearly due to extraneous causes (eg, concurrent disease, concomitant medications, disease under study, etc.)
- It does not follow a reasonable temporal sequence from administration of study drug
- It does not follow a known pattern of response to study drug
- It does not reappear or worsen when study drug is restarted
- An alternative explanation is likely but not clearly identifiable

Related

- An AE that is difficult to assign to alternative causes
- It follows a strong or reasonable temporal sequence from administration of study drug
- It could not be reasonably explained by the patient's clinical state, concurrent disease, or other concomitant therapy administered to the patient
- It follows a known response pattern to study drug
- It is confirmed with a positive rechallenge or supporting laboratory data

10.6.3 Outcome and Action Taken

The investigator will record the action taken and outcome for each AE according to the following criteria:

Action Taken with Study Drug

- None
- Dose reduced/delayed
- CO-1686 temporarily interrupted
- CO-1686 permanently discontinued
- Other (specify)

Outcome

- Recovered
- Recovered with sequelae
- Improved
- Ongoing

- Death
- Lost to follow-up

10.7 Follow-up of Adverse Events and Serious Adverse Events

All AEs occurring during the study are to be followed up in accordance with good medical practice until resolved; judged no longer clinically significant; or, if a chronic condition, until fully characterized through 28 days after the last dose of CO-1686. All SAEs must be followed until resolution or stabilization.

10.8 Regulatory Aspects of Serious Adverse Event Reporting

All SAEs, regardless of relationship to study drug, must be reported to the sponsor/safety designee within 24 hours of knowledge of the event, according to the procedures below. It is important that the investigator provide an assessment of relationship of the SAE to study treatment at the time of the initial report. The Clinical Trial Serious Adverse Event Report Form must be used for reporting SAEs.

While not considered an SAE, pregnancy occurring in a female patient or in the female partner of a male patient must also be reported to the sponsor/safety designee as soon as the event is known by the clinical site. If the pregnancy occurs in a female patient, study drug should be stopped immediately. Notification to the sponsor/safety designee should take place via facsimile or email utilizing the Pregnancy Report Form.

Further details on SAE/pregnancy reporting can be found in the Investigator's File.

Clovis or its designee is responsible for submitting reports of AEs associated with the use of the drug that are both serious and unexpected to the U.S. Food and Drug Administration (FDA), according to 21 Code of Federal Regulations (CFR) 312.32; to the Japanese Pharmaceuticals and Medical Devices Agency (PMDA); to the European regulatory authorities according to the European Commission (EC) Clinical Trials Directive (2001/20/EC); and to other regulatory authorities, according to national law and/or local regulations. All investigators participating in ongoing clinical studies with the study medication will receive copies of these reports for prompt submission to their IRB or IEC. In accordance with the European Commission Clinical Trials Directive (2001/20/EC), Clovis or its designee will notify the relevant ethics committees in concerned member states of applicable suspected unexpected serious adverse reactions (SUSARs) as individual notifications or through periodic line listings. Clovis or its designee will submit all safety updates and periodic reports to the regulatory authorities as required by applicable regulatory requirements.

11 STATISTICAL METHODS

11.1 Analysis Populations

The following analysis populations are defined for the study:

Tumor Evaluable Population—all patients who received at least 1 dose of CO-1686, have at least 1 measureable tumor lesion at baseline, and have at least 1 post-baseline tumor assessment as determined by the IRR.

Safety Population—all patients who have received at least 1 dose of CO-1686.

11.2 Statistical Methods

11.2.1 General Considerations

Data will be summarized by T790M status and by dose, but may also be pooled as appropriate.

Quantitative variables will be summarized using descriptive statistics (N, mean, standard deviation, median, minimum, and maximum) and/or frequency and percentages for medically relevant categories. Categorical variables will be presented using frequencies and percentages.

Kaplan-Meier methodology will be used to summarize PFS and OS.

All data will be used to their maximum possible extent but without any imputations for missing data.

All statistical analyses will be conducted with the statistical analysis software (SAS®) System.

11.2.2 Patient Disposition

The frequency and percentage of patients in each analysis population will be presented. The primary reason for discontinuation of CO-1686 will be summarized.

11.2.3 Baseline Characteristics

Baseline characteristics and demographic data will be summarized for the safety population.

11.2.4 Efficacy Analyses

The efficacy endpoints will be evaluated using RECIST Version 1.1 for the tumor evaluable population. Separate analyses will be performed for the assessments from the investigator and the independent reviewer.

PFS and OS will also be presented for the safety population.

11.2.4.1 Primary Endpoint

The primary endpoint of the study will be ORR according to RECIST Version 1.1. For Cohort A, ORR will undergo independent radiology review (IRR) and in Cohort B, scans will be assessed by IRR if needed as a supporting analysis.

The ORR is the best overall response recorded from the start of the treatment until disease progression or recurrence.

The frequency and percentages of patients with a best overall response of CR, PR, SD, or progressive disease (PD) will be summarized.

11.2.4.2 Secondary Efficacy Endpoints

BEST OVERALL RESPONSE

The frequency and percentages of best overall responses of CR, PR, SD, or PD will be summarized separately for T790M-positive and T790M-negative patients, and by dose.

DURATION OF RESPONSE

DR for CR and PR will be measured from the date that any of these best responses is first recorded until the first date that PD is objectively documented. DR will be summarized separately for T790M-positive and T790M-negative patients, and by dose, using descriptive statistics (N, mean, standard deviation, median, minimum, and maximum) as well as categorically. For patients who continue treatment post-progression, the first date of progression will be used for the analysis.

DISEASE CONTROL RATE

DCR is defined as the percentage of patients who have achieved CR, PR, and SD lasting at least 12 weeks.

PROGRESSION-FREE SURVIVAL

PFS will be calculated as 1+ the number of days from the first dose of study drug to documented radiographic progression or death due to any cause, whichever occurs first. Patients without a documented event of radiographic progression will be censored on the date of their last adequate tumor assessment (i.e., radiologic assessment) or date of first dose of study drug if no tumor assessments have been performed.

For patients who continue treatment post-progression, the first date of progression will be used for the analysis of PFS.

OVERALL SURVIVAL

OS will be calculated as 1+ the number of days from the first dose of study drug to death due to any cause. Patients without a documented date of death will be censored on the date the patient was last known to be alive.

POPULATION PK ANALYSES

Sparse blood sampling for POPPK analyses will be conducted in all patients treated with CO-1686. A specific POPPK data analysis plan will be developed and will outline the detailed approach to data handling, model development and diagnostics, individual model parameter estimation, exploration of covariate effects, and final model evaluation techniques.

QUALITY OF LIFE

QoL will be measured using the EORTC QLQ-C30, EORTC QLQ-LC13, and the DLQI.^{12,13}

The EORTC questionnaires will be scored using the published scoring algorithms provided by the EORTC. For each item or scale, a linear transformation will be applied to standardize the raw score to a range from 0 to 100. A high scale score represents a higher response level.

Thus a **high score for a functional scale** represents a *high / healthy level of functioning*, a **high score for the global health status / QoL** represents a *high QoL*, but a **high score for a symptom scale / item** represents a *high level of symptomatology / problems*.

The baseline QoL measurement will be defined as the last value prior to or on the day of the first dose of CO-1686. The on-treatment period will be defined as the day after the first dose of CO-1686 to 28 days after the last dose of CO-1686. QoL measurements collected during the on-treatment period will be included in the summary tables.

Evaluation of Symptoms

An improvement in symptoms will be defined as a ≥ 10 point decrease from baseline. A worsening in symptoms will be defined as a ≥ 10 increase from baseline. Patients with neither an increase nor a decrease will be considered stable. The frequency and percentage of patients categorized as an increase, stable, or decrease will be presented.

Time to Deterioration

The time to a worsening in symptoms will be computed as 1+ the number of days from the first dose of study drug to the first instance of a ≥ 10 point increase from baseline in symptoms.

The time to deterioration will be summarized using Kaplan-Meier methodology. Patients without a 10 point increase will be censored on their last evaluation.

Longitudinal Analysis

The summary of QoL data will include descriptive statistics (N, mean, standard deviation, minimum, median, and maximum) of the mean and/or percent change from baseline during the on-treatment period. Summaries using descriptive statistics of the change from baseline to each scheduled visit during the on-treatment period will be presented.

Graphical presentations may be used to present the mean changes over time.

11.2.4.3 Exploratory Endpoints

TIME-TO-TREATMENT FAILURE

The time-to-treatment failure will be computed as 1+ the number of days from the first dose of study drug to the last dose of study drug and will be presented with summary statistics.

EXTRA-CRANIAL PFS

In the subgroup of patients with brain metastases at baseline, extra-cranial PFS will be calculated as 1+ the number of days from the first dose of study drug to a 20% increase from nadir in the sum of the longest diameters of the extra-cranial target lesions.

Patients without extra-cranial progression will be censored on the day of their last tumor assessment.

CIRCULATING TUMOR DNA (CTDNA)

The presence of both the activating mutation and T790M at baseline and subsequent time points will be presented both as copies/mL plasma and mutant allele percentages and summarized with descriptive statistics.

COMPARISON OF BLOOD AND TISSUE RESULTS FOR T790M

The relationship between T790M detected in tumor compared with that detected in blood will be explored. This will involve determining the sensitivity, specificity, and positive and negative predictive values of blood with respect to tumor assuming that EGFR mutational status in tumor is a true reflection of tumor biology.

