9.5.2 Efficacy Evaluations

9.5.2.1 Tumor Assessments

Tumor assessments will be performed at Screening, and every 8 ± 1 weeks thereafter (Day 1 of Cycle 3, 5, 7 etc ± 1 week) until tumor progression, including at the End-of-Treatment Visit, if disease progression has not been documented previously. For patients with clinical progression, radiographic assessment should be performed to document evidence of radiographic progression. For a patient who discontinues treatment before progression, scans should continue until progression according to the protocol schedule. Exceptions to this requirement may be acceptable based on local institutional or regulatory requests and must be approved in advance by the sponsor. Scans will be evaluated locally for patient treatment decisions. Scans will be sent to a central radiological laboratory for independent response evaluation. In Cohort B, scans will be held at the central radiological vendor for later evaluation, assessed by IRR, if needed as a supporting analysis. Tumor response will be interpreted using RECIST Version 1.1 ([Appendix A](#)).¹¹

Patients who continue treatment with CO-1686 post-progression should continue to be scanned according to the protocol until they discontinue from the study.

Patients are required to have an end-of-treatment tumor scan using the same methodology used at Screening, **unless:**

- a) **Patient has radiographic evidence of disease progression while on study**
- or**
- b) **It has been < 2 weeks since last on-study scan**

In addition, an MRI may be used in place of CT at the end-of-treatment scan if required per local authorities.

Tumor assessments should consist of clinical examination and appropriate imaging techniques (preferably CT scans of the chest and abdomen, with appropriate slice thickness per RECIST Version 1.1); other studies (MRI and X-ray) may be performed if required. Imaging of the pelvis is required if clinically indicated eg, prior site of metastasis or symptomatic. The same methods used to detect lesions at baseline are to be used to follow the same lesions throughout the clinical study.

Brain imaging is required at baseline. In Cohort A, patients with brain lesions at baseline will require repeat brain imaging as part of the follow-up tumor assessments. In Cohort B, patients with brain lesions at Screening are not eligible for the study. Patients without baseline brain lesions do not require brain imaging on study unless clinically indicated.

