Stable Disease	Neither sufficient shrinkage to qualify for partial response nor sufficient increase to qualify for PD, taking as reference the smallest sum LD since the treatment started.
Progressive Disease	At least a 20% increase in the sum of the LD of target lesions, taking as reference the smallest sum on study (this includes the baseline sum if that is the smallest on study). In addition to the relative increase of 20%, the sum must also demonstrate an absolute increase of at least 5 mm. The appearance of one or more new lesions is also considered progression.

Evaluation of Non-target Lesions

Complete Response	Disappearance of all nontarget lesions and normalization of tumor marker level.
Stable Disease/Incomplete Response	Persistence of one or more nontarget lesion(s) or/and maintenance of tumor marker level above the normal limits.
Progressive Disease	Appearance of one or more new lesions and/or unequivocal progression of existing nontarget lesions.

If tumor markers are initially above the institutional ULN, they must normalize for a patient to be considered a complete *responder*.

Evaluation of Best Overall Response

The best overall response is the best response recorded from the start of the treatment until disease progression/recurrence (taking as reference for PD the smallest measurements recorded since the treatment started). The patient's best response assignment will depend on the achievement of both measurement and confirmation criteria.

Time Point Response

A response assessment will occur at the protocol-specified time points. The tables below provide a summary of the overall response status calculation at each time point for patients who have measureable and non-measureable disease (non-target disease only).

Time Point Response: Patients with Target (+/- Non-target) Disease			
Target Lesions	Nontarget Lesions	New Lesions	Overall Response
CR	CR	No	CR
CR	Non-CR/non-PD	No	PR
CR	Not evaluated	No	PR
PR	Non-PD or not evaluated	No	PR
SD	Non-PD or not evaluated	No	SD
Not Evaluated	Non-PD	No	NE
PD	Any	Yes or No	PD
Any	PD	Yes or No	PD
Any	Any	Yes	PD

NE = Not evaluable.

Evaluation of Best Overall Response When Confirmation of CR and PR Required		
Overall Response First Time Point	Overall Response Subsequent Time Point	Best Overall Response
CR	CR	CR
CR	PR	SD, PD or PR ^a
CR	SD	SD provided minimum criteria for SD duration met, otherwise, PD
CR	PD	SD provided minimum criteria for SD duration met, otherwise, PD

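### Extra-cranial PFS is defined by a 20% target-lesion rise alone: it leaves out new lesions, non-target progression, death and the 5 mm minimum, and so conflicts with the protocol's own RECIST 1.1 summary and PFS definition

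*Protocol*

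**What the plan says.** Section 11.2.4.3 of the protocol restricts the analysis as follows: "In the subgroup of patients with brain metastases at baseline". Time runs from first dose to "a 20% increase from nadir in the sum of the longest diameters of the extra-cranial target lesions". No second event is listed. The censoring rule is: "Patients without extra-cranial progression will be censored on the day of their last tumor assessment".

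Appendix A, the protocol's RECIST 1.1 summary, sets out progression more fully. For target lesions, besides the 20% rise, "the sum must also demonstrate an absolute increase of at least 5 mm", and "The appearance of one or more new lesions is also considered progression". For non-target lesions, progression is "Appearance of one or more new lesions and/or unequivocal progression of existing nontarget lesions". The PFS definition in Section 11.2.4.2 counts any radiographic progression and death of any cause.

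Section 11.2.4 opens with a general statement: "The efficacy endpoints will be evaluated using RECIST Version 1.1 for the tumor evaluable population". The SAP does not define extra-cranial PFS, and its Section 12 defers the exploratory objectives to study completion.

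The subgroup can come only from Cohort A: "In Cohort B, patients with brain lesions at Screening are not eligible for the study" (Section 9.5.2.1).

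**The concern.** The endpoint is called progression-free survival, but its rule is time to growth of the extra-cranial target lesions. A patient whose disease spreads to a new organ, whose non-target disease clearly worsens, or who dies has not failed under this rule unless the target sum also rises by 20%. Scheduled scans run until progression and continue afterwards only for patients who stay on treatment. A patient who progresses through a new or non-target lesion and then stops is therefore censored at or near the scan that shows the failure, so the censoring carries information about outcome.

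At stake is what the reported curve means. Read as extra-cranial PFS, it would miss several routes by which a patient can fail. Because a broader reading is also possible, two programmers could derive different endpoints from the same data.

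**Working it through.** The documents state no figure for this endpoint, so there is none to reproduce. The check compares the definitions, then works out direction and size.

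**1. Definitions side by side**

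| Component | Appendix A and Section 11.2.4.2 (PFS) | Section 11.2.4.3 (extra-cranial PFS) |
|---|---|---|
| Target sum up 20% from nadir | required | required |
| Absolute rise of at least 5 mm | required | absent |
| New lesion | event | not listed |
| Unequivocal non-target progression | event | not listed |
| Death | event | not listed |

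**2. Three illustrative patients** (cycles are 28 days; PFS is 1 plus days from first dose)

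- Stable targets, new liver lesion on the C5D1 scan. C5D1 is 4 × 28 = 112 days after first dose. PFS: event at 1 + 112 = 113 days. Extra-cranial PFS, if scanning then stops: censored at 113 days.
- Stable on the C3D1 scan, dies before C5D1. PFS: event at death. Extra-cranial PFS: censored at 1 + 2 × 28 = 57 days.
- Target sum 15 mm at nadir, later 18 mm. The rise is 3/15 = 20% but only 3 mm. Extra-cranial PFS: event. Appendix A: not progression on the target lesions.

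**3. Direction**

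Let A be the time to a 20% target rise, A5 the time to a rise of 20% and at least 5 mm, B the time to a new or non-target extra-cranial progression, and D the time to death.

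- The written rule uses A. Adding the omitted events gives min(A, B, D), which is never later than A. That part of the error is always upward.
- The full definition is min(A5, B, D). Since A is never later than A5, dropping the 5 mm condition can bring events forward. It matters only when 0.20 × nadir < 5 mm, that is, when the nadir is below 5/0.20 = 25 mm.
- For nadir sums of 25 mm or more, a 20% rise already meets the 5 mm condition and the net error is upward or zero. Below 25 mm it can go either way.

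**4. Size (illustration on assumptions, not from the documents)**

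Assume constant independent hazards, a fraction f of failures through the omitted routes, and censoring of those patients at that failure with no later counted target rise. The counted hazard is (1-f) times the full hazard, so the Kaplan-Meier median is multiplied by 1/(1-f):

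| f | 0.2 | 0.3 | 0.4 | 0.5 | 0.6 |
|---|---|---|---|---|---|
| Ratio of medians | 1.25 | 1.43 | 1.67 | 2.0 | 2.5 |

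With 8-weekly scans and an assumed true extra-cranial progression median of 8 months (8 × 4.345 = 34.8 weeks), leaving deaths aside, medians move to the next scan:

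- all extra-cranial progression counted: 34.8, read as 40 weeks;
- f = 0.2: 34.8 × 1.25 = 43.5, read as 48 weeks;
- f = 0.4: 34.8 × 1.67 = 58, read as 64 weeks;
- f = 0.6: 34.8 × 2.5 = 87, read as 88 weeks.

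A simulation of 20,000 patients gives the same four medians. Its 24-week progression-free rate is about 62% with all extra-cranial progression counted, against 68%, 75% and 83% for f = 0.2, 0.4 and 0.6. The 5 mm effect is not included in these figures.

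**The case against.** The best defence is that Section 11.2.4.3 sits under a section that applies RECIST 1.1 to all efficacy endpoints, and that its censoring sentence speaks of extra-cranial progression in general, not of the 20% rise. A programmer could fairly read this as full RECIST progression outside the brain. So it cannot be said that new and non-target lesions would never be counted in practice. The definition still needs repair. A general statement does not reliably add events to a specific numerical rule, it does not supply death, and the SAP offers no other definition.

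The size is also open to challenge. The documents give no value for f. Patients treated beyond progression keep being scanned, so a later target rise is still counted; where target growth soon follows the first failure, the inflation is smaller than 1/(1-f). This stands, and the ratios are illustrations only.

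The reach is small too. The endpoint has no test, power or decision rule, and development in NSCLC has been discontinued. Every omitted radiographic progression still counts in the main PFS. All of this stands and limits the importance of the point. The endpoint nevertheless remains in Sections 4.2.3 and 11.2.4.3.

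**Conclusion.** The definition as written conflicts with the protocol's RECIST 1.1 summary and PFS definition and should be corrected. Omitting new-lesion, non-target and death events biases time to event upward against the same rule with those events added. Some of these failures become censorings at or near the scan that shows them.

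A reader might go further and infer that the endpoint necessarily overstates control outside the brain. The documents do not support that for every patient, because the missing 5 mm condition works the other way for nadir sums below 25 mm. A reader might also infer that the gap between PFS and extra-cranial PFS would be presented as systemic benefit. Neither document plans that comparison or ties this endpoint to the objective on treatment beyond progression. Failures through target growth are counted, so such a gap would mislead only to the extent that failures came through the omitted routes.

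The inflation of up to about 1.25 times at f = 0.2 and 2.0 times at f = 0.5 rests on an assumed f, independent constant hazards and no later counted target rise. The effect is confined to one exploratory endpoint in Cohort A patients with baseline brain metastases. The primary ORR is untouched.

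**What to change.** In Section 11.2.4.3, define the event as the earlier of death from any cause and the first RECIST 1.1 progression outside the brain, where that progression is any of:

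- extra-cranial target sum up by at least 20% and at least 5 mm from nadir;
- a new extra-cranial lesion;
- unequivocal progression of extra-cranial non-target disease.

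State that brain-only progression is not an event, and whether such patients are followed on or censored at their last adequate extra-cranial assessment. Carry the same wording into the analysis plan for the completed study.

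If the narrow rule is intended, rename the endpoint time to extra-cranial target-lesion progression and say whether the 5 mm condition applies.

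The cost is one definition and one re-derived variable. Lesion site, target status and new lesions are already needed for RECIST reads, and deaths are already collected for OS. The downside for the sponsor is that the reported median will probably be less favourable.

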4.2.3 Exploratory Endpoints

- Time-to-treatment failure
- Extra-cranial PFS
- Change from baseline in mutant EGFR levels in ctDNA obtained from plasma
- Positive and negative percent agreement between blood and tissue results for T790M
- Identify biomarkers associated with response or resistance to CO-1686

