5 STUDY DESIGN

5.1 Overall Study Design and Plan

This is a Phase 2, single arm, open-label, dual cohort, multicenter study evaluating the safety and efficacy of CO-1686 administered PO BID to patients with previously-treated mutant EGFR NSCLC.

Patients will be enrolled into 2 cohorts. Cohort A will enroll approximately 125 eligible patients who are centrally confirmed T790M-positive and will be treated at 625 mg BID. Cohort B will be a continuation of the study and will enroll up to approximately 100 eligible patients who will be either centrally confirmed T790M-positive or T790M-negative. All patients in Cohort B will be treated at a starting dose of 500 mg BID. The priority for study enrollment will be for all T790M-positive patients to be enrolled into Cohort A first. Once Cohort A is complete, eligible T790M-positive patients will then be enrolled into Cohort B. All eligible T790M-negative patients will be enrolled into Cohort B.

All patients (for Cohort A and B) should have experienced disease progression while on treatment with the first single-agent EGFR-directed TKI (EGFR-TKI) therapy for advanced/metastatic NSCLC, and have had no intervening chemotherapy between EGFR-TKI and planned treatment with CO-1686. One line of chemotherapy prior to any EGFR-TKI treatment is permissible. The central laboratory will confirm that the patient's tumor harbors or does not harbor the T790M mutation using biopsy material obtained from either primary or metastatic tumor tissue within 60 days prior to dosing with study drug but after progression on EGFR-directed therapy.

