6 STUDY POPULATION

6.1 Number of Patients and Sites

The total enrollment planned for this study is approximately 225 patients. Patients will be enrolled into 2 cohorts:

Cohort A: Approximately 125 patients with centrally confirmed T790M-positive NSCLC will be enrolled. These patients will be treated at a dose of 625 mg BID.

Cohort B: Approximately 100 patients will be enrolled in order to include approximately 40 response evaluable, centrally confirmed T790M-negative patients. All Cohort B patients will be treated at a dose of 500 mg BID.

The priority for study inclusion will be for all T790M-positive patients to be enrolled into Cohort A first. Once this cohort is complete, eligible T790M-positive patients will then be enrolled into Cohort B. All eligible T790M-negative patients will be enrolled into Cohort B.

There will be approximately 90 investigative sites in the United States (US), Europe, Asia, and Australia.

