11.2.6 Exploratory Endpoints—Pharmacodynamic Analysis

An exploratory pharmacodynamic endpoint is the detection and quantification of mutant EGFR ctDNA in blood collected at baseline and with every tumor assessment. The presence of both the activating mutation and T790M at baseline and subsequent time points will be presented both as copies/mL plasma and mutant allele percentages. In addition, the relationship between T790M detected in tumor compared with that detected in blood will be explored. This will involve determining the sensitivity, specificity, positive and negative predictive values with 95% CIs of blood with respect to tumor assuming that EGFR mutational status in tumor is a true reflection of

tumor biology. The ctDNA from blood collected at these time points may also be assessed to identify biomarkers of response or resistance to EGFR-targeted therapy.

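### Pooled PPV and NPV of plasma T790M mix assay accuracy with an enrolment mix set by tissue status, so PPV reads high and NPV low against the protocol's own 60% background

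*Protocol*

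**What the plan says.** Protocol 4.2.3 lists the exploratory endpoint as "Positive and negative percent agreement between blood and tissue results for T790M". Predictive values are not in that list. Section 11.2.4.3 then plans sensitivity, specificity and the "positive and negative predictive values of blood with respect to tumor", taking the tissue result as the truth. Section 11.2.6 repeats the plan, with the "positive and negative predictive values with 95% CIs of blood with respect to tumor". Neither section names an analysis set or a prevalence, and neither mentions reweighting.

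Enrolment depends on the same tissue result:

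- Section 5.1: "Cohort A will enroll approximately 125 eligible patients who are centrally confirmed T790M-positive", and "The priority for study enrollment will be for all T790M-positive patients to be enrolled into Cohort A first".
- Section 6.1, on the total: "The total enrollment planned for this study is approximately 225 patients".
- Section 6.1, on Cohort B: "Approximately 100 patients will be enrolled in order to include approximately 40 response evaluable, centrally confirmed T790M-negative patients".
- Section 6.2: indeterminate, unknown or invalid tissue results do not qualify.

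The only analysis populations in section 11.1 consist of treated patients. The background in section 3.2 puts T790M at 60% of patients who progress on a TKI; the synopsis says approximately 60%.

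The SAP gives no method for the blood and tissue comparison. Its section 12 leaves the concordance objective until the study is completed.

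**The concern.** Sensitivity and specificity condition on the tissue result, so the numbers of tissue-positive and tissue-negative patients recruited do not shift them. PPV and NPV condition on the plasma result, so they depend directly on the tissue-positive share of the patients analysed. Here that share follows largely from cohort targets and enrolment order, not from who would come forward for testing after TKI failure.

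A reader would use NPV to judge whether a negative plasma result can be relied on without a biopsy, and section 9.1 says the blood samples may feed development of a plasma-based EGFR test. The planned 95% CI conveys sampling error only. It would not show that the centre of the interval has moved because of the enrolment mix.

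**Working it through.** The documents state no PPV, NPV, assay accuracy or sample size for this comparison, so there is no plan figure to reproduce. The enrolment figures are consistent: 125 + 100 = 225.

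**Inputs**

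- Cohort A 125, all tissue-positive; Cohort B 100; target of about 40 response-evaluable negatives (Protocol 5.1 and 6.1).
- Benchmark prevalence 60% (Protocol 3.2).
- Plasma accuracy is not given. Assumed: sensitivity (se) 70% and specificity (sp) 80% or 90%, with a wider set as a check.

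**Tissue-positive share.** The 40 is a target for evaluable negatives and not a cap, so the number of negatives enrolled is varied: π = (225 − negatives) / 225. For 40 negatives, 185/225 = 82.2%.

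**Formulas**

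- PPV = se·π / [se·π + (1 − sp)(1 − π)]
- NPV = sp(1 − π) / [sp(1 − π) + (1 − se)π]

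**Worked case: 40 negatives, se 70%, sp 80%.** Of 185 tissue-positives, 129.5 are plasma-positive and 55.5 plasma-negative. Of 40 tissue-negatives, 8 are plasma-positive and 32 plasma-negative. PPV = 129.5/137.5 = 94.2% and NPV = 32/87.5 = 36.6%. At 60% prevalence, PPV = 0.42/(0.42 + 0.08) = 84.0% and NPV = 0.32/(0.32 + 0.18) = 64.0%.

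**All mixes, se 70%, sp 80% / 90%**

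| Negatives enrolled | π | PPV | NPV | NPV shortfall from 60% benchmark (points) |
|---|---|---|---|---|
| 40 | 82.2% | 94.2 / 97.0 | 36.6 / 39.3 | 27 / 27 |
| 45 | 80.0% | 93.3 / 96.6 | 40.0 / 42.9 | 24 / 24 |
| 50 | 77.8% | 92.5 / 96.1 | 43.2 / 46.2 | 21 / 21 |
| 60 | 73.3% | 90.6 / 95.1 | 49.2 / 52.2 | 15 / 15 |
| Benchmark | 60% | 84.0 / 91.3 | 64.0 / 66.7 | – |

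**Other assumed accuracies, 82.2% mix against 60%**

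- se 50%, sp 90%: PPV 95.9% against 88.2%; NPV 28.0% against 54.5%.
- se 80%, sp 70%: PPV 92.5% against 80.0%; NPV 43.1% against 70.0%.
- se 90%, sp 90%: PPV 97.7% against 93.1%; NPV 66.1% against 85.7%.
- An uninformative test (se 50%, sp 50%) would still show a PPV of 82.2%.

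Across the informative accuracies tried, the 82.2% mix raises PPV by about 3 to 14 points and lowers NPV by about 20 to 27. The direction is the same for any informative assay.

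**By cohort.** In Cohort A alone π = 1, so PPV is 100%, NPV is 0% for any imperfectly sensitive assay, and specificity cannot be estimated. Cohort B alone is 60/100 = 60% positive with 40 negatives, which matches the benchmark, but 50% with 50 negatives and 40% with 60.

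**The case against.** The strongest reply is that the measures unaffected by the mix are already planned. With tissue as reference, sensitivity and specificity are positive and negative percent agreement. Section 4.2.3 lists those as the endpoint, and 11.2.6 gives all four measures 95% CIs. PPV and NPV are two further descriptive figures beside them. This stands, and it limits the point to those two figures.

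A reader might infer that the predictive values would reflect enrolment quotas and not test performance at all. The documents do not support that for pooled data, where the values depend on both accuracy and mix; it is true only for Cohort A alone. Nor do they fix the positive share at 82%. The 40 counts response-evaluable negatives, and section 5.1 sends every eligible negative to Cohort B, so more may enrol. The 27-point NPV shortfall is therefore the top of the range in the table.

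The analysis set is also not stated. Section 9.5.4 speaks of matched screening samples from each patient, and including screen failures would reduce the problem. No such set is defined, however, and section 11.1 offers only treated patients.

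Section 11.2.1 summarises data by T790M status and by dose, with pooling optional. Summarised by dose, Cohort B could sit near 60%, but only if about 40 negatives enrol, and Cohort A is then degenerate.

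Finally, the analysis is exploratory. Entry uses tissue, no planned decision uses plasma PPV or NPV, and development in NSCLC has been discontinued. That limits the consequence but does not correct the numbers.

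**Conclusion.** The point holds for pooled PPV and NPV. If 11.2.4.3 and 11.2.6 are followed in treated patients, the tissue-positive share is about 73% to 82% against the protocol's 60%, and nothing in either document adjusts for it. At an assumed sensitivity of 70% and specificity of 80% to 90%, PPV is overstated by about 4 to 10 points (for example 95.1 − 91.3 = 3.8 and 94.2 − 84.0 = 10.2), and NPV is understated by about 15 to 27 points.

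The sizes rest on three assumptions: the assay accuracy, the number of negatives enrolled (40 to 60), and analysis of treated patients. The benchmark is the protocol's background figure, not a measured prevalence among patients screened here. Percent agreement is not shifted by the mix, and neither the primary response analysis nor eligibility is affected.

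**What to change.** In Protocol 11.2.4.3 and 11.2.6, and in the SAP text for the final analysis:

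1. Make positive and negative percent agreement, with exact 95% CIs, the reported measures, as 4.2.3 already lists, and name the analysis set.
2. Either drop raw pooled PPV and NPV, or compute them by Bayes' rule from percent agreement at a stated prevalence (about 60%, with a range) and label them as standardised.
3. Use the prevalence among patients screened by the central laboratory only if those results are available.

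Items 1 and 2 change analysis wording only and need no new samples. Item 3 may cost more: section 13.5 requires an eCRF for each enrolled patient, and no screened-patient dataset is defined.

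The downside is that standardised predictive values rest on an assumed prevalence. They also inherit the imprecision of negative agreement: 32 of 40 gives 80% with an exact 95% CI of 64.4% to 90.9%. Showing a range of prevalences makes the first dependence visible.
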